## 8.4 Statistical Analysis Plan

This is a Simon 2 stage Phase II prospective clinical trial. The statistical plan will be for an optimal 2 stage design with the  $P_0=0.6$  and  $P_1=0.8$ . If <30 responses are seen then the experimental hypothesis has been rejected. The type 1 error is 0.0489 and the power is 0.8024. The probability of early stopping if the response rate is  $P_0=20.5\%$

### 8.4.1 Analysis of Primary Endpoints

The primary efficacy endpoint of the study is the objective response rate (ORR), which is defined as the proportion of subjects for whom the best overall response by week 12 at the time of data cutoff is confirmed CR or PR as per RECIST. RECIST version 1.1 will be used in this study for assessment of tumor response. While either CT or MRI may be utilized, as per RECIST 1.1, CT is the preferred imaging technique in this study. In the primary analysis, point estimates of ORR and 95% confidence intervals will be provided. Subjects who do not have any post-baseline tumor assessments will be considered as non-responders. Supportive analysis of ORR may be performed to include response based on investigator assessment. If sufficient responses are observed, additional supportive analyses may be conducted in subgroups defined by baseline characteristics.

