## 5 Treatment Plan

### 5.1 Dosage and Administration

**Table 1 Regimen Description**

Drug	Dose/Potency	Dose Frequency	Route of Administration	Regimen/Treatment Period	Use
Pembrolizumab	200 mg	Q3W	IV infusion	Day 1 of each 3 week cycle	Experimental
Ipilimumab	1 mg/kg	Q3wk X4	IV infusion	Day 1 of each 3 wk cycle, for 4 cycles	experimental
Aspirin	975 mg	PO BID	oral	Each day	experimental

Trial treatment should begin on the day of randomization or as close as possible to the date on which treatment is allocated/assigned.

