### 5.2 Timing of Dose Administration

Trial treatment should be administered on Day 1 of each cycle after all procedures/assessments have been completed as detailed on the Trial Flow Chart (Section 6.0). Trial treatment may be administered up to 3 days before or after the scheduled Day 1 of each cycle due to administrative reasons.

All trial treatments will be administered on an outpatient basis.

Pembrolizumab 200 mg will be administered as a 30 minute IV infusion every 3 weeks. Sites should make every effort to target infusion timing to be as close to 30 minutes as possible. However, given the variability of infusion pumps from site to site, a window of -5 minutes and +10 minutes is permitted (i.e., infusion time is 30 minutes: -5 min/+10 min).

Ipilimumab, 1 mg/kg will be administered for 4 cycles as a 60 minute intravenous infusion following the pembrolizumab. No premedication is used routinely. If any infusion reaction is suspected, the infusion may be stopped and antihistamines may be administered (Benadryl 50 mg PO or 25 mg IV) and the infusion restarted.

Aspirin, 975 mg PO Twice daily is taken orally by the patient. An adequate number of pills will be dispensed every 3 weeks and pill counts done to ensure compliance

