### **6.2.7 Tumor Imaging**

Prefer imaging of chest/abdomen and pelvis. PET/CT, CT, or MRI are acceptable. Imaging to be performed every 12 weeks (every 4 cycles).

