## Appendix 1 Schedule of Study Procedures and Assessments

Trial Period:	Screening Phase a	Treatment Cycles b								End of Treatment e	Post-Treatment Follow-up f
						To be repeated beyond 8 cycles					
Treatment Cycle/Title:	Main Study Screening	1	2	3	4	5	6	7	8	End of Treatment (EOT) visit	Safety Follow-up Visit
		-28 to -1	± 3	± 3	± 3	± 3	± 3	± 3	± 3		30 days post discon
Administrative Procedures											
Informed Consent	X										
Inclusion/Exclusion Criteria	X										
Demographics and Medical History	X										
Prior and Concomitant Medication Review	X										
Post-study anticancer therapy status										X	X
Survival Status										X	X
Trial Treatment Administration											
Ipilimumab		X	X	X	X						
Pembrolizumab		X	X	X	X	X	X	X	X		
Aspirin		X	X	X	X	X	X	X	X		
Clinical Procedures/Assessments											
Review Adverse Events		X	X	X	X	X	X	X	X		X
Full Physical Examination	X	X	X	X	X	X	X	X	X		X
Vital Signs and Weight	X	X	X	X	X	X	X	X	X		X
ECOG Performance Status	X	X	X	X	X	X	X	X	X		X
Laboratory Procedures/Assessments											
Pregnancy Test – Urine or Serum-HCG c	X										
PT/INR and aPTT	X										
CBC with Differential	X	X	X	X	X	X	X	X	X		
Comprehensive Serum Chemistry Panel	X	X	X	X	X	X	X	X	X		
Urinalysis	X										
T3, FT4 and TSH	X	X	X	X	X	X	X	X	X		
Tumor Tissue Collection g	X										
Efficacy Measurements											
Tumor Imaging d	X				X				X		

a. Screening procedures to be completed within 28 days of C1D1, except laboratory tests for screening should be performed within 10 days prior to the first dose of treatment.

- b. Patients will take aspirin daily and receive pembrolizumab and ipilimumab every 3 weeks for 4 cycles. After 4 cycles, ipilimumab will be discontinued and patients will continue receiving pembrolizumab every 3 weeks while taking aspirin daily.
- c. Women of childbearing potential: negative urine or serum pregnancy test within 72 hours prior to receiving trial treatment. If urine test is positive or non-confirmatory, a serum pregnancy test will be required.
- d. Prefer imaging of chest/abdomen and pelvis. PET/CT, CT, or MRI are acceptable.

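### The scan that decides the week-12 response rate has two dates in the plan, about week 9 and week 12, and the by-week-12 limit has no window

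*Combined protocol and SAP*

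**What the plan says.** - **Endpoint.** Section 8.4.1 counts a subject as a responder if "the best overall response by week 12 at the time of data cutoff is confirmed CR or PR as per RECIST". Sections 2.1, 8.1 and 8.2.1 use the same week-12 limit. None of them expresses week 12 in days or attaches an assessment window.
- **Imaging, text.** Section 6.2.7: "Imaging to be performed every 12 weeks (every 4 cycles"). It states no window for imaging.
- **Imaging, flow chart.** The row "Tumor Imaging" in Appendix 1 is marked at Screening, Cycle 4 and Cycle 8. The cycle columns carry a window of plus or minus 3 days. The row's footnote covers only anatomy and modality: "Prefer imaging of chest/abdomen and pelvis. PET/CT, CT, or MRI are acceptable".
- **Order of procedures.** Section 5.2: "Trial treatment should be administered on Day 1 of each cycle after all procedures/assessments have been completed as detailed on the Trial Flow Chart". It also allows treatment up to 3 days either side of the scheduled Day 1 for administrative reasons.
- **Cycle length.** Table 1 places pembrolizumab on "Day 1 of each 3 week cycle".
- **Stage-1 count.** Section 8.3 counts CR or PR at a decision point at least 4 months after the start of treatment. The stage-1 count in section 8.2.1 has no week-12 limit.
- **Missing scans.** Section 8.4.1 makes non-responders of subjects with no post-baseline assessment. It has no rule for a scan taken shortly after week 12.

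**The concern.** One scan decides the primary endpoint for most patients, because the next scheduled scan comes 12 weeks later on either reading. Its date should therefore be unambiguous. The flow chart, read with the rule that procedures precede the Day 1 dose, points to a date three weeks before the endpoint's limit. The text of section 6.2.7 points to the limit itself.

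Three things follow:

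1. If the flow chart is followed, the trial reports a week-9 rate under a week-12 label.
2. If different patients are scanned under different readings, one ORR mixes two time points.
3. If the 12-week text is followed, a visit inside the permitted window can land just after an endpoint limit that has no window of its own.

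Where responders go uncounted, observed ORR falls against a fixed 60% null, and the final Simon decision is made on the lower count.

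**Working it through.** **1. Scan dates.** Inputs: 21-day cycles (Table 1) and procedures before the Day 1 dose (section 5.2). Elapsed days to Day 1 of cycle c = 21 × (c − 1). Study day = elapsed days + 1.

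| Visit | Elapsed days | Study day | Weeks elapsed |
|---|---|---|---|
| Cycle 4 Day 1 | 63 | 64 | 9.0 |
| Cycle 5 Day 1 | 84 | 85 | 12.0 |
| Cycle 8 Day 1 | 147 | 148 | 21.0 |
| Cycle 9 Day 1 | 168 | 169 | 24.0 |

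- Appendix 1 with section 5.2: first scan at week 9.0 (plus or minus 3 days gives 60 to 66 elapsed days, weeks 8.6 to 9.4), next at week 21.
- Section 6.2.7: first scan at week 12.0, next at week 24.
- The Cycle 4 and Cycle 8 marks are 12 weeks apart, but treatment start to the Cycle 4 visit is only 9.

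**2. The window on the week-12 reading.** Section 6.2.7 gives no imaging window. If the visit window of plus or minus 3 days is borrowed, permitted scans fall on elapsed days 81 to 87 (weeks 11.6 to 12.4). Days 85, 86 and 87 are past 84 elapsed days. The plan does not say whether a first response seen then counts.

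**3. Confirmation.** Section 8.4.1 requires a confirmed response, but the second scheduled scan is at week 21 or 24. Scheduled imaging cannot confirm a response by week 12 on either reading. Only the reference to data cutoff in that sentence could let confirmation come later. Four months is about 4 × 30.4 / 7 = 17.4 weeks, so the stage-1 decision can also come before the second scheduled scan.

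**4. The plan's own operating characteristics.** Inputs: p0 = 0.60, p1 = 0.80 (sections 8.1 and 8.4); stop if 7 or fewer of 11 respond (sections 3.1 and 8.3); reject the null at 31 or more of 43. Sections 8.2.1 and 8.4 do not word the final rule consistently. The rule used here is the one that reproduces the stated error rates.

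- P(stop at stage 1) = P(Bin(11, p) ≤ 7)
- P(reject) = Σ over x = 8 to 11 of P(Bin(11, p) = x) × P(Bin(32, p) ≥ 31 − x)

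At p = 0.60: stop 0.704, reject 0.0489. At p = 0.80: stop 0.161, reject 0.8024. Section 8.4 states 0.0489 and 0.8024; section 8.2.1 states 70% and 16% for early stopping. All agree.

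**5. Sensitivity to uncounted responders.** Let f be the fraction of responders not counted, so the observed rate is p × (1 − f). The documents give no value for f, so it is an assumption. The loss is applied at both stages.

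| f | Observed rate, true 80% | Power | Stage-1 stop, true 80% | Observed rate, true 60% | P(reject), true 60% |
|---|---|---|---|---|---|
| 0 | 0.800 | 0.802 | 0.161 | 0.600 | 0.049 |
| 2% | 0.784 | 0.744 | 0.198 | 0.588 | 0.036 |
| 5% | 0.760 | 0.64 | 0.260 | 0.570 | 0.021 |
| 10% | 0.720 | 0.442 | 0.372 | 0.540 | 0.008 |

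The stage-1 column belongs to the week-9 reading only, and then only if the decision is taken before the week-21 scan. On the week-12 reading a scan up to 3 days late is well inside the 4 months of section 8.3, so the stage-1 count need not lose it. With stage 1 unaffected, the power loss for a given f would be no larger than shown.

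**The case against.** The strongest reply is that this is an ambiguity and not a demonstrated error. Much of that stands.

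- **Cycle 4 Day 1 is an inference.** Appendix 1 marks a cycle, not a day. Section 5.2 is mainly about when treatment is given. Section 6.2.7 equates 12 weeks with 4 cycles, and the Cycle 4 mark is compatible with a scan at the end of that cycle. This stands. The point is that the documents support two dates, not that week 9 is established.
- **A week-9 response is a response by week 12.** Nothing seen at week 9 is misclassified; later responses are simply not looked for on schedule. Section 6 also allows unscheduled procedures if clinically necessary, so some could still be found.
- **No hard cut-off is stated.** A reader might infer that 3 of 7 permitted scan days (43%), or 4 of 7 (57%) if week 12 ends on study day 84, fall outside the endpoint. That needs an exclusion rule that no section states and scan days spread evenly over the window. A sensible analyst would count an in-window scan.
- **Patients treated exactly on schedule.** A reader might also infer that these patients lose responses on the week-12 reading. They reach Cycle 5 Day 1 at exactly 84 elapsed days. They would be affected only if week 12 ended on study day 84, which the documents do not say.
- **Direction of error.** Lost responders lower the false-positive rate as well as power. Whether the comparison with 60% is unfair also depends on when response was assessed in the study cited for the null, which the documents do not report.

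What the reply does not remove is the conflict of dates. A team following the flow chart could scan three weeks earlier than a team following section 6.2.7, and both would be following the protocol.

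**Conclusion.** The concern holds as a conflict between passages about the scan that decides the primary endpoint: about week 9 (day 64) then week 21, or week 12 (day 85) then week 24. Under the flow-chart reading the reported ORR is in effect a week-9 rate. Under the 12-week reading responders can be miscounted, depending on a cut-off the plan leaves undefined. That second part is close to missing detail.

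The size cannot be derived from the documents. The power figures are scenarios for an assumed f, not estimates. They show only that the design is sensitive: an undercount of 5% would take power at a true ORR of 80% from 0.802 to about 0.64.

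A reader might go further and conclude that observed ORR is biased down on either reading and that false stage-1 stopping rises on both. The documents do not support this. The bias on the week-12 reading needs an unstated cut-off, and section 8.3's 4-month count means the stage-1 rates do not carry over to that reading. The plan should be corrected before responses are counted.

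**What to change.** Reconcile Appendix 1 with section 6.2.7, then tie the endpoint to the result:

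1. State the first on-treatment scan once, in days from Cycle 1 Day 1 and with its own imaging window, at a date consistent with the week-12 endpoint. Use the same wording in both places.
2. In section 8.4.1, define by week 12 as at or before that scheduled assessment, including its window.
3. State whether the required confirmation may come from a later scan.
4. Apply the same definition to the stage-1 count in sections 8.2.1 and 8.3.

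The length of the window is for the sponsor to set and justify; the documents contain none for imaging.

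The cost is one edit to the schedule table and a few sentences. The timing change adds no scans. If the scan moves from the Cycle 4 visit, the first tumour assessment comes up to 3 weeks later than Appendix 1 read literally. That delays the first look at response and also at progression, on which continued treatment depends under section 3.4.

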## 8 Statistical Analysis Plan

### 8.1 Statistical Analysis Plan Summary

This is a non-randomized prospective Phase II clinical trial with a Simon stage II design with an early stopping provision. The primary objective is to evaluate the overall response rate (ORR) by week 12 in patients with stage III unresectable/stage IV melanoma. The hypothesis is that the study treatment regimen will have a clinical meaningful improvement in ORR by week 12. H0 is for an ORR by week 12 = 60% while Ha is for an ORR by week 12= 80%. 60% is used as a threshold for the H0 based on published data (19).

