### 8.2 Sample Size and Accrual Rate Considerations

#### 8.2.1 Sample Size and Power Estimate

A two-stage Simon's optimal design is used for the study to test the null hypothesis that the ORR by week 12 is 60% or less versus the alternative hypothesis that the ORR by week 12 is greater than 80% using an one-sided test with 5% level of significance with the power of 80% for alternative hypothesis. An initial 11 evaluable patients will be accrued at the end of stage 1. If at least 4 or more overall responders (CR/PR per RECIST 1.1) from stage 1 are observed, the study will continue to enroll additional 32 evaluable patients in the stage 2. The null hypothesis will be rejected at the 5% level of significance (one-sided) if there are 30 or fewer ORR by week 12 among all 43 evaluable patients by the end of stage 2. If the ORR rate is 60%, the probability of ending the study during the first stage is 70%; if the ORR rate is indeed 80%, the probability of study will be terminated at the first stage is 16%. The significance level of the study is 0.05 and the power is 0.80 for the study design.

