### 8.3 Interim Analyses and Stopping Rules

The two stage sequential design of this study has a decision timepoint based on the counts of CR or PR (per RECIST 1.1) from stage 1 by at least 4 months post-initial treatment regimen of the 11 patients with measurable disease at baseline, to either stop or initiate stage 2 of the study. In the first stage 11 patients will be accrued. If  $\leq 7$  responses are seen here then the trial will be stopped

for futility. If >7 responses are seen then the trial will be continued an a full 43 patients will be enrolled.

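### The 95% interval planned for ORR does not match the one-sided 5% two-stage test: at 31 of 43 responses H0 is rejected, yet every usual 95% interval contains 60%

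*Combined protocol and SAP*

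**What the plan says.** All of the following is in the combined protocol and SAP.

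- **Estimation.** Section 8.4.1 gives the whole plan for the primary estimate: "In the primary analysis, point estimates of ORR and 95% confidence intervals will be provided". No section names an interval method, says whether the interval is one- or two-sided, plans a p-value, or mentions an adjustment for the two-stage design.
- **Hypotheses.** Section 8.1: "H0 is for an ORR by week 12 = 60% while Ha is for an ORR by week 12= 80" per cent.
- **Test.** Section 8.2.1: "using an one-sided test with 5% level of significance with the power of 80% for alternative hypothesis". Section 8.4 confirms the type of design: "The statistical plan will be for an optimal 2 stage design with the" null and alternative rates of 0.6 and 0.8. It gives a type I error of 0.0489 and a power of 0.8024.
- **Stage 1.** Section 8.3: "In the first stage 11 patients will be accrued", and "If >7 responses are seen then the trial will be continued an a full 43 patients will be enrolled". Section 3.1 agrees. Section 8.2.1 differs: "If at least 4 or more overall responders (CR/PR per RECIST 1.1) from stage 1 are observed", the study goes on.
- **Final rule.** Section 8.2.1 rejects the null at 30 or fewer responses among 43, which is the reverse of what a test for a higher rate needs. Section 8.4 counts the trial as failed below 30, which read literally makes 30 a success. Neither section states 31.

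**The concern.** The decision rule and the planned interval use different error levels. The lower limit of a two-sided 95% interval spends 2.5% in the lower tail, while the test spends 5%. A conventional binomial interval also treats the 43 patients as a single fixed sample, although a trial reaches 43 only after passing stage 1.

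For both reasons the interval can contain 60% when the test has rejected 60%. This happens at the smallest successful counts, where readers will look hardest at the interval. A report would then state that the null was rejected beside a primary interval that includes the null, with no sentence in the SAP to say how the two relate.

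**Working it through.** **Inputs.** p0 = 0.60 and p1 = 0.80 (section 8.1); 11 patients in stage 1, continuing if more than 7 respond (sections 3.1 and 8.3); 32 more patients, 43 in total (section 8.2.1).

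**Step 1: reproduce the plan's error rates.** Let X1 be Binomial(11, p) and X2 be Binomial(32, p). The probability of continuing and ending with at least s responses is

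U(s, p) = sum over x = 8 to 11 of P(X1 = x) × P(X2 ≥ s − x).

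With s = 31:

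- p = 0.60: 0.0205 + 0.0181 + 0.0086 + 0.0017 = 0.0489.
- p = 0.80: U = 0.8024.
- Probability of stopping at stage 1: 0.704 at 60% and 0.161 at 80%, matching the 70% and 16% in section 8.2.1. (The 20.5% in section 8.4 does not match. It coincides with the expected sample size under the null, 11 + 0.2963 × 32 = 20.48, and is not used here.)

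The alternatives fail. Success at 30 or more gives a type I error of 0.0794. Continuing at 4 or more of 11, with success at 31, gives 0.0695. Among the readings of the text, only more than 7 of 11 with at least 31 of 43 fits both stated figures.

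**Step 2: p-values at the boundary.** The two-stage exact one-sided p-value is U(s, 0.60): 0.0489 at 31 and 0.0271 at 32. Both reject.

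**Step 3: conventional two-sided 95% intervals (%).**

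| Method | 31/43 (72.1%) | 32/43 (74.4%) |
|---|---|---|
| Clopper-Pearson | 56.3-84.7 | 58.8-86.5 |
| Wilson | 57.3-83.2 | 59.8-85.1 |
| Agresti-Coull | 57.2-83.4 | 59.6-85.2 |
| Jeffreys | 57.6-83.8 | 60.1-85.6 |
| Wald | 58.7-85.5 | 61.4-87.5 |

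At 31 all five contain 60%. At 32 the first three do. At 33 none does (lowest limit: Clopper-Pearson, 61.4%).

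**Step 4: separate the two causes.** Two-stage limits solve U(s, p) = a for the lower limit and 1 − U(s + 1, p) = a for the upper. Use a = 0.025 for a 95% interval and 0.05 for a 90% interval.

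| Lower limit (%) | 31/43 | 32/43 |
|---|---|---|
| 90%, Clopper-Pearson | 58.7 | 61.2 |
| 95%, two-stage | 57.6 | 59.7 |
| 90%, two-stage | 60.1 | 62.2 |

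At 32, moving to 90% is enough and the two-stage adjustment alone is not, so the conflict there comes from the level alone. At 31 neither change is enough by itself. Besides Clopper-Pearson, the plain 90% Wilson (59.8%), Agresti-Coull (59.7%) and Jeffreys (59.98%) limits also fall below 60%; only Wald (60.8%) clears it.

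The full two-stage 90% intervals are 60.1-86.9% at 31 and 62.2-87.4% at 32. At 30, which is not a success under the inferred rule, the lower limit is 58.1%. The lower limit therefore passes 60% at the same count at which the test rejects.

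**Step 5: how often.** The probability of a given final count is U(s, p) − U(s + 1, p).

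- True ORR 80%: 0.0398 / 0.8024 = 5.0% of successes fall on 31; (0.0398 + 0.0668) / 0.8024 = 13.3% on 31 or 32.
- True ORR 75%: 0.0784 / 0.5916 = 13.3%; (0.0784 + 0.0986) / 0.5916 = 29.9%.

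**Step 6: point estimates at 31/43.** Simple proportion 72.1%. Median-unbiased estimate 73.2% from U(31, p) = 0.5, or 74.0% in its mid-p version. UMVUE 79.3%.

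**The case against.** The strongest reply is that the count decides the trial. Sections 8.2.1 and 8.4 base the conclusion on the number of responders and make no interval a criterion, so a 95% interval can be read as description. That stands: a reader might infer that the interval could overturn the result, and the documents do not support that. It does not remove the problem, because section 8.4.1 places the interval in the primary analysis, plans no p-value there, and does not call the interval descriptive.

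Four other strong readings also go too far.

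- **That the plan chose an unadjusted two-sided interval.** The text is silent on method and sidedness. Those are default readings, and the only stated feature is the 95% level.
- **That any trial with 32 responses would show the conflict.** With Jeffreys or Wald it would not. Only the result at 31 holds for all five methods.
- **That the cause is neglect of the two-stage design.** At 32 it is the level alone. At 31 it is both.
- **That the simple proportion is biased low and should be replaced.** Over all trials its mean is 56.2% at a true 60% and 77.6% at a true 80%. Among trials that reach stage 2, the only ones that can end at 31 or 32 of 43, its mean is 64.5% and 81.0%, so the bias is upward.

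It is also fair to object that 31 appears nowhere in the documents. If 30 counted as a success, the two-stage 90% lower limit there (58.1%) would fall below 60% and the agreement would fail. The final rule therefore has to be settled first.

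**Conclusion.** The concern holds in a limited form. The stated 95% level does not match the one-sided 5% test. If success starts at 31 of 43, a trial with 31 responses rejects the null and reports a primary interval that contains it, whichever usual two-sided method is used. At 32 this depends on the method, which the plan leaves open until after the data are seen. The share of successes affected is 5% (31 alone) to 13% (31 or 32) at a true ORR of 80%, and 13% to 30% at 75%.

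This is a defect of reporting. The decision rule, the sample size and the error rates are untouched. It should still be corrected, because the contradiction follows from the plan's stated level and the remedy is nearly free.

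The conclusion assumes a boundary of 31 inferred from the stated error rates, a two-sided reading of the interval, and exactly 43 patients analysed. Section 8.2.3 allows up to 50 to be enrolled and section 8.2.2 does not replace patients with missing data, so the attained number could differ and the limits would change.

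**What to change.** First reconcile the final rule in sections 8.2.1 and 8.4, and the stage 1 rule in sections 8.2.1 and 8.3, with the stated error rates. Then amend section 8.4.1 along these lines:

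- Report the exact one-sided p-value for the two-stage design.
- Report a two-sided 90% confidence interval computed on the two-stage sample space for the stage sizes actually attained. Its lower limit is the one-sided 95% bound and, with the boundary at 31 of 43, exceeds 60% exactly when the null is rejected.
- Label any 95% interval as descriptive and name its method.
- Keep the simple proportion as the reported estimate. If a design-adjusted estimate is added, name one in advance, for example the median-unbiased estimate in a stated version (73-74% at 31/43). Leaving a choice between that and the UMVUE (79.3%) would put 5 to 6 points of discretion into the primary estimate.

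The cost is a short SAP amendment and a small program, with no new data. The drawback is that the interval is less familiar than a plain binomial one, and its 90% level needs a sentence of explanation in the report.
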